## STATISTICAL CONSIDERATIONS

### Sample Size and Randomization

Figure 1 illustrates the flow of participants through the study and estimated total sample sizes during each study phase based on prior data. The overall effectiveness of the intervention will be evaluated based on the primary outcome measure, which is total medication count. Based on current enrollment rate, we estimate that approximately 144 patients per year will enroll in the study, or 576 across all four years of enrollment. Among those, we estimate that 27.5% will either die or otherwise be lost from the study prior to the 90-day post PAC discharge follow up period. Thus, across all four years of enrollment, an estimated 420 patients will contribute measurements at 90 days. Although 567 is the expected total enrollment, we conservatively use 420 to estimate the statistical power associated with the assessment of overall effectiveness (i.e., overall completion rate) rather than enrollment rate, to account for estimated attrition across all study phases.

Preliminary data is available for the effect of deprescribing on the reduction in the counts of total medications. Our pilot intervention (N=40) was associated with roughly a 50% reduction in the count of total medications from enrollment to hospital discharge, whereas a roughly 25% reduction was observed in the control group receiving routine hospital care. Using these preliminary data and mixed-effects Poisson regression methods, we implemented a simulation-based power analysis wherein we assumed that this effect would be attenuated by 20% at SNF discharge, and again by 20% at the 90-day follow up. Using a sample size of 420, there is greater than 95% power to detect a 50% versus 25% reduction in total medications. There is approximately 90% power to detect a 30% versus 25% reduction in total medications, and 80% power to detect a 27.5% versus 25% reduction in total medications. Thus, the target sample size provides some protection against effects that are substantially smaller than that observed in our preliminary data.

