Participants will be randomized in a 1:1 ratio using permuted blocks of two or four, where the size for each block is selected uniformly at random. This type of randomization ensures balance across the intervention and control groups after every second or fourth randomization (depending on the size of the current block). This randomization scheme will be generated by computer using the Mersenne-Twister pseudo random number.

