## Safety Analyses

All-cause mortality will be quantified by the count of deaths per person-months (28 days) of observation by intervention/usual care group. These values will be computed overall and stratified by study phase. Thus, the maximum follow-up period for mortality (and other safety outcomes) is 90 days after SNF discharge. Cox proportional hazards regression will be used to quantify statistical uncertainty about the effect of intervention on

the hazard of death (overall and separately within study phase), which will be summarized using the hazard ratio and corresponding Wald-type 95% confidence interval.

The incidence and timing of (potentially recurrent) adverse events will be quantified, for each type of event both overall and stratified by study phase, by counting the number and fraction of affected participants, by tabulating the number of events per participant, and the total number of events per person-months. The effect of the intervention on the hazard of each adverse event type (overall and separately within study phase) will be quantified using Cox proportional hazards regression in a recurrent events (frailty) configuration, which accounts for between-subject heterogeneity in the baseline hazard of recurrent events. In other words, this approach accounts for the within-subject correlation among recurrent event times. The hazard ratio will be summarized using a Wald-type 95% confidence interval.

If there are sufficiently many events, the Nelson-Aalen estimator of the baseline hazard will be used in conjunction with the estimated hazard ratio to estimate median survival with Wald-type 95% confidence interval, for each type of adverse event. Graphical regression diagnostics will be used to evaluate model fit and modeling assumptions of the Cox proportional hazards method.

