Pharmacokinetic and Pharmacodynamic Changes: Medication cessation may additionally alter pharmacokinetic and pharmacodynamic profile of medications. This may include medications that inhibit or potentiate the cytochrome P450 enzyme inhibitor, thus altering clearance of specific medications. Alternatively, some medications may have opposing effects on blood pressure or electrolytes (e.g., potassium). All deprescribing actions will be made by a trained pharmacist and clinicians. In the case that there is believed to be a potential change in pharmacokinetics or pharmacodynamics, deprescribing pharmacists / NPs will alert the primary medical team and make recommendations for surveillance of symptoms, signs (e.g., vital signs), labs (e.g., electrolytes, INR), or follow-up tests (e.g., EKG). Medications can be restarted or increased at any time should adverse pharmacokinetic or pharmacodynamics effects be detected.

Medical Condition Exacerbation: The most expected side effect of deprescribing is the return of the condition for which the medication was initially prescribed. A medication may be intentionally reduced or discontinued in the

absence of symptoms or signs to determine if the medication is still required to maintain control of a medical condition. In the Graves et al. study, 88% of all ADWEs were due to medical condition recurrence. Published data, however, does suggest that medication deprescribing for specific conditions (e.g., hypertension, osteoporosis, hyperlipidemia, angina) can be done without serious adverse effects. A strength of this trial is that we will be able to monitor for exacerbations of medical conditions in a post-acute care setting (mean length of stay = 26.9 days), where monitoring of vital signs and symptoms are done daily by licensed nurses. In addition, during the “SNF handover” process, all discontinued medications will be clearly delineated along with any expected signs or symptoms that may be expected to return. In addition, any necessary laboratory or diagnostic study follow-up will be recommended, as necessary. Medications can be restarted or increased at any time should condition signs or symptoms recur.

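### The safety plan's median survival for each adverse event type is not expected to be usable for death and, for non-fatal events, comes out too early because no method accounts for death

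*Combined protocol and SAP*

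**What the plan says.** The Safety Analyses section handles all-cause mortality by death rates per person-month and a Cox hazard ratio. It handles recurrent adverse events by the number and share of participants affected, events per participant, event rates, and a Cox model with frailty. It then adds that, given enough events, a Nelson-Aalen baseline hazard combined with the hazard ratio will be used "to estimate median survival with Wald-type 95% confidence interval, for each type of adverse event". No threshold for enough events is given.

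The same section states that "the maximum follow-up period for mortality (and other safety outcomes) is 90 days after SNF discharge". Sample Size and Randomization expects that "27.5% will either die or otherwise be lost from the study prior to the 90-day post PAC discharge follow up period".

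Three further places bear on the point:
- Safety Monitoring and Assessments counts unexpected death (outside hospice) as an adverse event, so the median sentence can be read to cover death.
- Safety and Healthcare Utilization Outcomes withdraws participants who move to hospice.
- Nothing in the safety plan says how death or hospice withdrawal is handled when other events are analyzed.

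**The concern.** A median time to event can be reported only if the curve falls to 50% while enough people are still under observation. A condition on event number does not secure that, because many events can accumulate in a large trial with the curve still well above 50%.

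For hospitalization, emergency visits and adverse drug withdrawal events (ADWEs) the difficulty is different. Censoring at death is acceptable for a cause-specific hazard ratio. Converting that hazard into a probability or a median describes a population in which nobody dies first. In this older, ill population the result puts the point at which half have had the event too early. If mortality differs between arms, the distortion differs between arms as well.

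The recurrent-event model adds an ambiguity. Its baseline hazard is conditional on the frailty and covers repeat events. The plan does not say whether the median is for the first event or for the gap between events, or whether it is for a participant of average frailty or for the whole arm.

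At stake is how clearly the absolute safety result can be read in a trial whose main risk is harm from withdrawing drugs.

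**Working it through.** **Inputs**
- Enrollment (Sample Size and Randomization): "approximately 144 patients per year will enroll in the study, or 576 across all four years of enrollment".
- Death plus all other loss: 27.5% (same section). The split is not given, so mortality is ranged from 5% to 27.5%.
- Completers (same section): "an estimated 420 patients will contribute measurements at 90 days".
- Allocation (same section): "Participants will be randomized in a 1:1 ratio using permuted blocks of two or four", so 576 / 2 = 288 per arm.
- Post-acute stay (Approach to potential risks of the proposed study): "mean length of stay = 26.9 days". Average follow-up from post-acute admission is 26.9 + 90 = 116.9 days. Hospital days before that are ignored.

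**Step 1. The plan's own figure.** 576 × (1 − 0.275) = 417.6, which agrees with 420 to within rounding. The section also prints 567 as the expected enrollment (567 × 0.725 = 411.1); nothing below turns on this.

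**Step 2. Death.** Let a share d die and a share c be lost otherwise, with d + c = 0.275. For a common follow-up time, Kaplan-Meier survival is lowest when all losses precede all deaths: S = 1 − d / (1 − c). At a constant hazard the median is ln 2 × 116.9 / (−ln S).

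| d | Deaths of 576 | Lowest S | Median, days |
|---|---|---|---|
| 5% | 28.8 | 0.9355 | 1,215 |
| 10% | 57.6 | 0.8788 | 627 |
| 20% | 115.2 | 0.7838 | 333 |
| 27.5% | 158.4 | 0.7250 | 252 |

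Even if every loss were a death, an arm would have 288 × 0.275 = 79.2 deaths, against 144 for half.

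A simulation of 4,000 arms of 288 per scenario checked the effect of unequal follow-up. With a fixed 116.9 days, no arm reached 50%. With exponential or lognormal post-acute stays (mean 26.9 days), the tail of the curve crossed 50% in 32% to 37% of arms if all attrition was death, and in 8% to 11% if half was. Typically only 2 to 3 patients were then at risk, so such a median is a tail artefact.

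**Step 3. Non-fatal events.** Assume constant cause-specific hazards λe (event) and λd (death), and write T for 116.9 days. The death-censored risk is 1 − exp(−λe T). The cumulative incidence is λe / (λe + λd) × [1 − exp(−(λe + λd) T)]. The time by which half have had the event is −ln[1 − 0.5(λe + λd)/λe] / (λe + λd). Set λe so that the death-censored risk is 50% at 116.9 days (λe = ln 2 / 116.9), and set λd = −ln(1 − d) / 116.9.

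| Assumed mortality d | Death-censored risk | Cumulative incidence | Time to half, days (116.9 if death is censored) |
|---|---|---|---|
| 5% | 50% | 48.9% | 120.9 |
| 10% | 50% | 47.7% | 125.6 |
| 20% | 50% | 45.4% | 138.0 |
| 27.5% | 50% | 43.5% | 151.7 |

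The overstatement is 1.1 to 6.5 percentage points. In each row a median would be reported at 116.9 days although fewer than half would have had the event by then.

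**Step 4. Scale from the plan's own event rate.** PAC Handover and Ongoing Deprescribing estimates 20% readmission to the study hospital directly from post-acute care. Carrying that hazard forward (an assumption) gives λe = −ln(0.8) / 26.9 = 0.0083 per day. Take an assumed λd = 0.0015 per day, which is 1 − exp(−0.0015 × 117) = 16% mortality over 117 days. The death-censored median is ln 2 / 0.0083 = 84 days; with death as a competing event it is 91 days. At 117 days the two risks are 62% and 58%.

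**The case against.** The strongest reply is that this is a conditional, secondary summary on which no decision depends. That is largely right. The data and safety monitoring board is directed to the relative hazard and its confidence interval, and those are untouched. The reply lowers the priority of the point. It does not make the planned median a good summary.

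A reader might infer several stronger things that the documents do not support:
- **That the plan commits to a median outright.** It does so only if there are enough events. The guard is weak, since up to about 158 deaths could satisfy it with survival still at 72.5%, but it is there.
- **That the sentence clearly covers death.** All-cause mortality has its own paragraph with no median. Death enters only through the definition of an adverse event, and then only as unexpected death.
- **That a median time to death is impossible.** The 27.5% is a planning estimate, and with unequal follow-up a curve can drift below 50% in its tail. Not expected to be usefully estimable is as far as the figures go.
- **That the plan states death will be censored.** It is silent. Censoring is what the named method does by default.
- **That no absolute safety information is planned.** The plan tabulates the share affected, events per participant and rates. Apart from incomplete follow-up, the share affected is an observed cumulative incidence. What is not planned is a risk by arm at a stated time, with a difference and an interval.
- **That a frailty model can have no median.** It can, once the event time and the frailty level are specified.

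**Conclusion.** The point holds in a limited form. The named method gives no usable median for death on the plan's own attrition figure: expected survival is at least about 72.5%, and the median is 252 days or later at a constant hazard, against about 117 days of average follow-up. For non-fatal events the method gives a median that is too early, by 4 to 35 days in the Step 3 setting (120.9 − 116.9 and 151.7 − 116.9) and by about 7 days in Step 4 (91 − 84). The bias is real but modest.

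The result for death rests on the 27.5% holding. The result for other events rests on constant hazards and on a mortality figure that the documents do not give. The hazard ratios, crude rates and shares affected are not in question. This is a cheap improvement to a secondary summary, not a flaw in the trial's safety monitoring.

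**What to change.** In Safety Analyses:
1. Replace median survival with cumulative incidence by arm, and the arm difference with 95% CI, at pre-specified times that include the end of the planned follow-up.
2. Use Kaplan-Meier for death, and Aalen-Johansen with death as a competing event for first hospitalization, first emergency visit and first ADWE.
3. State how hospice withdrawal is treated in each of these analyses.
4. Report a median only where the curve crosses 50% with adequate numbers at risk, and say which event time it describes.
5. Keep the hazard ratios and the planned tabulations.

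The cost is SAP wording and a little more analysis work with standard software. No new data are needed.

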## Data Analyses

Missing Data: We have extensive preliminary data describing attrition due to mortality which should not differ between the intervention and control groups. However, we cannot exclude the possibility that missing data will be associated with intervention. We will examine the incidence of missing data by group. If imbalances are found, we will implement a series of sensitivity analyses, using multiple imputations, to assess the degree of bias that might be induced by missing data.

Randomization, intent-to-treat, and safety outcomes: Participants will be assigned to the usual care control group or the intervention group in a completely randomized fashion (i.e., without blocking or stratification). The effectiveness of randomization will be assessed by summarizing the balance of baseline demographic and clinical factors across randomization groups. The sample mean, standard deviation, and five-number summary will be used to summarize continuous variables. The count and proportion will be used to summarize categorical variables. All randomized patients who complete Phase 2 (i.e., discharged to a partner SNF) will be included in analyses. We will implement both intent-to-treat and per-protocol analyses.

Repeated measures: Barring study withdrawal or death, each participant will be assessed at multiple time points. We anticipate that such repeated measurements will exhibit correlations across time points. Our statistical plan takes full advantage of this information by using a mixed-effects framework for each analysis. In the event that a mixed-effects technique cannot be implemented, an alternative method will be used and the standard errors of effect estimates will be adjusted using the Huber-White ‘sandwich’ method.

Limitations: The proposed intervention will be implemented during hospitalization and will continue during the patient’s SNF stay because there is a high probability that new medications, including PIMs, will be added during these care transitions. However, we acknowledge that new medications also might be added after PAC discharge; thus, we have incorporated intervention components that should, at least partially, mitigate this problem. Specifically, we will communicate with pharmacies and known community providers so that they are aware of the patient’s preferences and final discharge medication list. We also will determine during the 7-day post PAC follow-up if intervention patients are taking medications that were previously stopped but which are still in the home. We will assess changes in medications for both intervention and control patients for 90 days post PAC discharge and, thus, be able to determine if intervention components need to be extended past PAC discharge.

The randomization of patients prior to hospital discharge, as opposed to randomization by PAC discharge location, has numerous advantages and is necessary because it is not possible to determine which PAC a patient

will ultimately go prior to implementing the deprescribing intervention. This approach does, however, increase the risk of contamination because both intervention and control group participants will be discharged to the same PACs; thus, there is a possibility that PAC providers will change their medication practices for control participants as a result of our active monitoring of medication changes for the intervention participants. We will be able to detect such contamination effects by comparing changes in the medication lists from hospital to PAC discharge for both intervention and control groups, with the expectation of fewer changes in the intervention group. We believe the risk for contamination is minimal as there was no evidence of contamination effects in our pilot intervention, and PAC providers will not be asked to actively deprescribe beyond following the deprescribing actions recommended by the research team, many of which will be initiated prior to hospital discharge. Finally, PAC and hospital providers may not be equipped to overcome many of the barriers to deprescribing that will be addressed with our Shed-MEDS protocol.

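### Missing-data sensitivity analyses run only if missingness rates differ between arms; a prespecified, unconditional tipping-point analysis of the 90-day medication count would be a cheap improvement

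*Combined protocol and SAP*

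**What the plan says.** Under Statistical Considerations, Data Analyses, the Missing Data paragraph states one diagnostic, "We will examine the incidence of missing data by group", and one consequence: "If imbalances are found, we will implement a series of sensitivity analyses, using multiple imputations". It sets no threshold or test for an imbalance and does not compare reasons for loss, its timing or its predictors. It describes "attrition due to mortality which should not differ between the intervention and control groups", although it then concedes that missingness could be associated with the intervention. It does not say what the imputation model would assume.

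Under Sample Size and Randomization the plan gives the expected loss, "we estimate that 27.5% will either die or otherwise be lost from the study prior to the 90-day" follow-up, and concludes that "an estimated 420 patients will contribute measurements at 90 days". Under Outcomes, Hypotheses 1a-1b are tested with a mixed-effects Poisson model with a random intercept, and the intervention effect is reported at each time point, including 90 days. No other section supplies a missing-data sensitivity analysis that runs regardless of balance. The per-protocol analysis that is also planned does not address loss to follow-up.

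**The concern.** Bias in the 90-day comparison depends on who is missing in each arm and why, and the number missing does not reveal that. A rule keyed to the rate will skip the check whenever the two arms lose similar proportions, even if the participants lost differ between arms in ways the model cannot see. For deaths, balanced loss is what the plan itself expects.

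The 90-day count is a named time point of the Aim 1 hypotheses, and the power statement is built on 90-day completers. If the rule is not triggered, the 90-day conclusion rests on a missing-at-random assumption with no planned test. If it is triggered, the value of the result depends on an unstated choice: an imputation that assumes missing at random would largely repeat what the mixed model already assumes.

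**Working it through.** **Inputs.** From Sample Size and Randomization: 576 enrolled ("approximately 144 patients per year will enroll in the study, or 576 across all four years of enrollment"), 27.5% lost before 90 days, 420 with 90-day data, 1:1 allocation (288 per arm), and contrasts of 50%, 30% and 27.5% reduction against 25%. From Overview and Objectives: a mean of 14 medications at hospital discharge in the preliminary cohort. Assumptions: list sizes of 14 to 25, the share of loss due to death, and all simulation variances.

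**1. The plan's own figure.** 576 × (1 − 0.275) = 417.6, which agrees with 420 after rounding. The section also prints 567 as expected enrollment (567 × 0.725 = 411.1); this does not affect the point. Expected loss is 0.275 × 576 = 158.4, about 158 participants.

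**2. Does equal loss protect the estimate?** Simulation of 1,000 trials per scenario: 288 per arm, exactly 27.5% missing at 90 days in both arms, no true effect. The model was a random-intercept linear model on log counts, as a stand-in for the mixed Poisson model. Assumed inputs: baseline mean 14, and log-scale SDs of 0.3 between patients and 0.2 between visits.

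| What drives loss | Mean 90-day rate ratio (RR) | False rejection |
|---|---|---|
| Chance | 0.999 | 5.9% |
| Earlier observed counts, opposite directions by arm | 0.999 | 5.6% |
| Unseen 90-day count, same way in both arms | 1.002 | 5.2% |
| Unseen 90-day count, intervention arm only | 0.902 | 68% |
| Unseen 90-day count, opposite by arm, weaker | 0.888 | 82% |
| Unseen 90-day count, opposite by arm, stronger | 0.799 | 100% |

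The trigger stays silent in all six rows because the rates are identical. In the second row, missing participants averaged 1.24 times the observed count in the intervention arm and 0.80 times in control, yet the model recovered the truth. Only a difference that earlier counts do not predict does damage. The last three mechanisms are strong (missing intervention participants average 1.31 to 1.64 times the observed), so the sizes are illustrative.

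**3. Tipping ratio if the full 27.5% could be shifted.** With equal loss d, and k the ratio of missing to observed mean count in each arm:

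full-sample RR = observed RR × (1 − d + d·k_I) / (1 − d + d·k_C).

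Setting k_C = 1 and the result to 1 gives k_I = (1/RR − 0.725)/0.275.

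- 27.5% vs 25%: RR = 0.725/0.75 = 0.967; k_I = (1.0345 − 0.725)/0.275 = 1.125.
- 30% vs 25%: RR = 0.70/0.75 = 0.933; k_I = (1.0714 − 0.725)/0.275 = 1.26.
- 50% vs 25%: RR = 0.50/0.75 = 0.667; k_I = (1.5 − 0.725)/0.275 = 2.82.

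Given step 2, read k_I as excess beyond what the earlier counts predict.

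**4. Allowing for deaths.** If half the loss is death (assumption), the fraction of survivors missing is 0.1375/(1 − 0.1375) = 0.1375/0.8625 = 15.9%. The smallest powered effect on a list of M drugs is 0.025 × M, so the cancelling shift is 0.025 × M/0.159:

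- M = 14: 0.35/0.159 = 2.2 drugs.
- M = 25: 0.625/0.159 = 3.9 drugs.

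These shifts bring the point estimate to null; statistical significance would be lost at a smaller shift.

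**5. Sensitivity of the trigger to rates.** The plan names no test. If a 5% two-sided comparison of proportions were used with 288 per arm, a true 5-point difference in missingness would be flagged with 27% power and a 10-point difference with 77%.

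**The case against.** Much of the case on the other side stands. The primary model is a likelihood-based mixed model that uses the repeated counts, and it copes well with loss that follows observed history. Deaths by arm are already analysed under Safety Analyses, with rates and Cox hazard ratios. Surrogate interviews (Study Procedures) and the pharmacy record review before the 90-day visit (Primary Outcomes - Medications) may reduce missing medication data. None of this supplies an unconditional check, but it lowers the stakes.

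A reader might infer four stronger things that the documents do not support.

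- That the 90-day result will be biased. Bias at equal rates needs arm-specific dependence on unseen counts, and nothing in the plan shows this will occur.
- That intervention participants will leave because stopped drugs are restarted. Restarts are permitted, but no section links them to dropout. The intervention ends at discharge from post-acute care, both arms then follow the same schedule, and restarts during that stay should appear in the discharge count the model uses.
- That the planned imputation cannot test the assumption. The text does not say that it is missing-at-random, and the remedy below is itself multiple imputation. The fair criticism is that it is unspecified.
- That a shift of 1.3 to 2.3 drugs would cancel the smallest powered effect (0.025 × 14/0.275 and 0.025 × 25/0.275). This applies the shift to all 27.5%, which includes deaths and losses from every phase, whereas the analysed population is participants discharged to a partner facility. The shiftable fraction is smaller, by an amount the documents do not give.

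One objection cuts the other way. The power simulation attenuates the pilot effect by 20% at SNF discharge and again at 90 days. If the 2.5-point contrast is attenuated likewise, the range in step 4 is multiplied by 0.8 × 0.8 = 0.64, giving about 1.4 to 2.5 drugs.

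**Conclusion.** The point holds as a cheap improvement; it is not an error that invalidates the analysis. The trigger looks at rates, and equal rates cannot establish that the missing participants are alike, so the plan can skip its only sensitivity analysis when one is needed.

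How much this matters depends on the effect observed. A result near the small end of the power statement would be fragile. A pilot-sized effect would survive anything short of an implausibly large difference, and the analysis would then strengthen the conclusion. The drug-count range rests on an assumed half share of deaths, assumed list sizes and an unattenuated contrast. The simulated biases rest on assumed variances and mechanism strengths. That the trigger cannot see differences in who is missing depends on none of these.

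**What to change.** In the Missing Data paragraph, delete the condition on imbalance and prespecify the following for the 90-day medication count in the analysed population:

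- Always run multiple imputation with a delta shift for intervention participants lost alive, for example +1, +2 and +3 drugs added to imputed values, continuing until significance is lost, and report that shift.
- State the imputation model and what it assumes at delta zero.
- Do not impute counts after death. Present the deaths by arm already planned under Safety Analyses beside the result.

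The cost is a few lines of SAP text and modest programming. No new data are needed, and the sample size and primary model are unchanged. The downside is one more table, which may make the 90-day result look less certain.
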